13 DATA HANDLING AND RECORD KEEPING

All procedures for the handling and analysis of data will be conducted using good computing practices meeting ICH and US FDA guidelines for the handling and analysis of data for clinical trials.

13.1 Data Entry

Study-specific data that have been outlined in the protocol will be entered into the clinical database by individual(s) designated by the Investigator.

13.2 Data Quality Control and Reporting

Data are verified electronically using a series of programmed edit checks that have been created by the Clinical Data Manager and programmed by the Clinical Data Programmer or designee. Data discrepancies will be brought to the attention of the clinical team and investigated by the clinical research associate (CRA) and site staff. CRAs will review and verify a targeted subset of data collected in the eCRF against source documentation during remote review or scheduled monitoring visits. The specific data selected for source data verification will be detailed in Clinical Monitoring Plan. The CRA will work closely with the site staff to address any discrepancies that have been found so that proper resolutions can be made and documented in the clinical database. An audit trail within the system will track all changes made to the data.

13.3 Archiving of Data

Archived versions of the database will be saved by Ocuphire consistent with ICH GCP guidelines, complying with whichever of the requirements is longer. Ocuphire will notify the Investigator when documents should be returned.

13.4 Records Retention

The Investigator's site and clinical laboratory will retain all records related to the study in compliance with ICH GCP guidelines.

13.5 Amendments to the Protocol

Modifications of the signed protocol are only possible by approved protocol amendments and with the agreement of all responsible persons. The procedure for approval of a protocol amendment is identical to that for approval of the protocol. The IRB must be informed of all protocol amendments and should be asked for its opinion as to whether a full re-evaluation of the ethical aspects of the study is necessary by the committee. This should be fully documented.

The Investigator must not implement any deviation from or change to the protocol, without discussion with and agreement by Ocuphire and prior review and documented approval/favorable opinion of the amendment from the relevant ethics committee, except where it is necessary to eliminate an immediate hazard to study subjects, or where the change(s) involves only logistical or administrative aspects of the study (e.g., change in monitor, change of telephone number).

[figure not shown]
Protocol amendments will be submitted to the appropriate authority(ies) as required by the applicable regulatory requirement(s).

APPENDIX 1: IRIS COLOR CHART

Study enrollment includes both light and dark-colored eyes. Examples of [REDACTED]
[REDACTED] and [REDACTED] for the purposes of this study are detailed in the
chart below.

[figure not shown]

[figure not shown]
APPENDIX 2: VISUAL ACUITY CHARTS

BCDVA (distance) will be measured with a Standard [REDACTED]
[REDACTED]

Distance High-Contrast Chart

Distance Low-Contrast Chart

DCNVA will be measured under [REDACTED]

[figure not shown]
[REDACTED] (letters recorded, later converted to logMAR and number of lines).

Near High-Contrast Chart

[figure not shown]
APPENDIX 3: SUBJECT QUESTIONNAIRE

Please use the pictures below to answer the questions in the following table.

[figure not shown]

Representative Images of Dim Light Disturbances

1. Circle the number below to describe the severity of your symptoms at night

2. In terms of overall severity, how

[figure not shown]

3. Please circle all of the statements below that apply to your level of avoiding driving at night due to dim light vision disturbances?

[figure not shown]

- D. I only drive at night when I know the exact routes
- E. Occasionally I miss a social outing because it would require me to drive at night
- F. I have no problems when I drive at night

[figure not shown]
4. For the following statements, **circle the number to indicate to what extent does dim light vision disturbance impact your day-to-day life.**

[figure not shown]
5. **I am satisfied with my night vision at the moment.**

[figure not shown]
6. **My night vision has improved.**

7. **My night vision is 100% back to normal.**

8. Please indicate the [REDACTED]
[REDACTED])

[figure not shown]

APPENDIX 4: ADRENERGIC AND CHOLINERGIC DRUGS

The following drugs are examples of drugs which cannot be used within 7 days prior to screening, or during the study unless the drug, dose and regimen has been consistent for the 7 days prior to screening. *This list is not inclusive of all drugs in these classes. If there is any doubt, please consult with the Medical Monitor.*

Alpha-1-agonists Methyl norepinephrine Naphazoline Oxymetazoline Tetrahydrozoline Phenylephrine Xylometazoline	Non-selective alpha-antagonists Phenoxybenzamine Tolazoline Labetalol Carvedilol	Acetylcholine receptor agonists Pilocarpine (M ₃ receptors)	Gastrointestinal atropine belladonna
Alpha-2-agonists Brimonidine Clonidine Guanfacine Guanabenz Guanoxabenz Guanethidine Xylazine Tizanidine Methyldopa	Alpha-1-antagonists Alfuzosin Prazosin Doxazosin Tamsulosin Terazosin	Acetylcholine receptor antagonists Scopolamine Dicycloverine Tolterodine Oxybutynin Ipratropium Mamba Toxin (MT ₇) Pirenzepine Telenzepine	Parkinsonism amantadine benztropine biperiden trihexyphenidyl

APPENDIX 5: SCREENING PROCESS FOR INCLUSION/EXCLUSION CRITERIA

**APPENDIX 6: CONJUNCTIVAL HYPEREMIA GRADING SCALE USING IMAGES
FROM CCLRU**

2. LIST OF ABBREVIATIONS AND DEFINITION OF TERMS

Only abbreviations and terms relevant to the SAP are repeated herein. The reader is referred to the protocol for the complete and comprehensive list of abbreviations and definitions of terms for the study.

| Abbreviation/Term | Definition |
|-------------------|---|
| ADaM | Analysis Data Model |
| AE | adverse event |
| ANCOVA | analysis of covariance |
| ARP | All Randomized Population |
| ATC | Anatomical Therapeutic Chemical |
| BAT | Brightness Acuity Tester |
| BCDVA | best-corrected distance visual acuity |
| BP | blood pressure |
| CCLRU | Cornea and Contact Lens Research Unit |
| CDISC | Clinical Data Interchange Standards Consortium |
| CI | confidence interval |
| CRF | Case Report Form |
| CSR | Clinical Study Report |
| DCNVA | distance-corrected near visual acuity |
| DD | drug dictionary |
| DLD | dim light vision disturbances |
| EDC | electronic data capture |
| ETDRS | Early Treatment Diabetic Retinopathy Study |
| HR | heart rate |
| IOP | Intraocular pressure |
| ITT | Intention-To-Treat |
| LOCF | last observation carried forward |
| logMAR | logarithm of the minimum angle of resolution |
| LSM | least squares mean |
| MAR | missing at random |
| MCMC | Markov Chain Monte Carlo |
| MedDRA | Medical Dictionary for Regulatory Activities |
| mHCVA | mesopic high-contrast visual acuity |
| mITT | Modified Intention-To-Treat |
| Nyxol | Phentolamine Mesylate Ophthalmic Solution 1% (Nyxol®) |

| Abbreviation/Term | Definition |
|--------------------------|-------------------------------------|
| OD | right eye |
| OPD | optical path difference |
| OR | odds ratio |
| OS | left eye |
| OU | both eyes |
| PD | pupil diameter |
| pLCVA | photopic low-contrast visual acuity |
| PP | Per Protocol |
| PT | preferred term |
| QD | once daily |
| RMS | root-mean square |
| SAE | serious adverse event |
| SAP | Statistical Analysis Plan |
| SDTM | Study Data Tabulation Model |
| SE | standard error |
| SOC | system organ class |
| SP | Safety Population |
| TEAE | treatment-emergent adverse event |
| TFL | tables, figures, and listings |
| VA | visual acuity |
| WHO | World Health Organization |

3. INTRODUCTION

3.1. Preface

This document presents a statistical analysis plan (SAP) for Ocuphire Pharma, Inc. Protocol OPI-NYXDLD-301 (LYNX-1) (*Randomized, Placebo-Controlled, Double-Masked Study of the Safety and Efficacy of Nyxol (0.75% Phentolamine Ophthalmic Solution) in Subjects with Dim Light Vision Disturbances*).

Reference materials for this statistical plan include the protocol OPI-NYXDLD-301 amendment 3 (29JUN2021) and Case Report Forms (CRFs) Version 3.0 (02AUG2021).

The SAP described hereafter is an *a priori* plan. The SAP will be finalized and approved prior to unmasking of any study data.

For the reasons stated here, the conduct of the study in the field is considered to be independent of any study outcome that might materialize upon enactment of the currently proposed statistical plan.

3.2. Purpose of Analyses

The LYNX-1 study is a randomized, parallel arm, double-masked, placebo-controlled study of the safety and efficacy of Nyxol (0.75% Phentolamine Ophthalmic Solution) to evaluate the efficacy of Nyxol to improve mesopic low-contrast visual acuity (mLCVA) in subjects with dim light vision disturbances (DLD).

The Sponsor intends to use this first Phase 3 registration study to evaluate Nyxol for the

Post-hoc exploratory analyses not identified in this SAP may be performed to further examine the study data. These analyses will be clearly identified, where appropriate, in the final clinical study report (CSR). Additional analyses not prospectively identified in this SAP may also be completed for publications, or regulatory or funding inquiries. These analyses, if performed, may not be reported in the CSR but will be fully detailed in the document containing the additional analyses.

3.3. Summary of Statistical Analysis Changes to the Protocol

A hierarchical analysis was added to formally test a family of endpoints beyond the primary efficacy endpoint. Otherwise, the study protocol includes the subject questionnaire as both an efficacy and safety endpoint; in this analysis plan, all subject questionnaire endpoints are treated as efficacy variables. Also, two secondary efficacy endpoints were added:

Otherwise, the analyses described in this analysis plan are consistent with the analyses described in the protocol.

4. STUDY OBJECTIVES AND ENDPOINTS

Study objectives and endpoints defined in the protocol include safety and efficacy endpoints. Objectives and pre-specified endpoints are as follows:

4.1. Study Objectives

The objectives of this study are as follows:

- To evaluate the efficacy of Nyxol to improve mLCVA in subjects with DLD
- To evaluate the efficacy of Nyxol to improve visual performance
- To evaluate the safety of Nyxol
- To evaluate any additional benefits of Nyxol in treating DLD subjects

4.2. Study Endpoints

4.2.1. Primary Endpoints

The primary efficacy endpoint is the percent of subjects with ≥ 15 Early Treatment Diabetic Retinopathy Study (ETDRS) letters (≥ 3 lines) of improvement in the study eye compared to baseline in monocular mLCVA at Day 8.

4.2.2. Secondary and Exploratory Endpoints

Secondary endpoints for efficacy and safety assessments include the following:

Efficacy:

Secondary efficacy endpoints (for the study eye, the non-study eye, the best of either eye, and binocular) include:

- [REDACTED]
- [REDACTED]
- [REDACTED]
- [REDACTED]
- [REDACTED]

| Term | Percentage |
|-------------------------|------------|
| Climate change | 98 |
| Global warming | 100 |
| Green energy | 95 |
| Carbon footprint | 92 |
| Sustainable development | 90 |
| Renewable energy | 88 |
| Emissions reduction | 85 |
| Green economy | 82 |
| Carbon tax | 95 |

Exploratory efficacy endpoints (for the study eye, the non-study eye, and the best of either eye) are collected and analyzed for the sites that have an optical path difference (OPD) Scanner and include but are not limited to:

- [REDACTED]

In addition,

Efficacy Measurements:

- PD is measured with a [REDACTED]
- mLCVA is measured under [REDACTED] (letters recorded, converted to logMAR).
- pLCVA is measured under [REDACTED] (letters recorded, converted to logMAR).
- DCNVA is measured under mesopic conditions by a high-contrast Near Visual Acuity Chart [REDACTED]
- Best-corrected distance visual acuity (BCDVA) is measured under mesopic conditions by a [REDACTED] at [REDACTED] (letters recorded, converted to logMAR).

- [REDACTED]
- Subject questionnaire is a brief symptom survey.

Safety and Tolerability:

- Conjunctival hyperemia
- Adverse events (AEs)
- Vital signs (heart rate [HR] and blood pressure [BP])
- Intraocular pressure (IOP)
- Biomicroscopy
- Ophthalmoscopy
- Dry eye measurements
- Urine pregnancy tests for females of childbearing potential

Safety Measurements:

- Conjunctival hyperemia is assessed visually with a grading scale (0-3) using images from the Cornea and Contact Lens Research Unit (CCLRU).
- IOP is measured with the Tono-Pen.
- BP and HR is measured manually or with available digital devices.

5. STUDY METHODS

5.1. General Study Design and Plan

A sample size of approximately 160 DLD subjects \geq 18 years of age were randomized in a 1:1 ratio to Nyxol or placebo, with the expectation that approximately 136 subjects were evaluable for efficacy, where evaluable means receiving at least 1 dose of study medication and having a Baseline and a Day 8 mLcVA measurement.

[REDACTED]. The subjects were recruited from approximately 15 investigational sites.

Following the successful completion of screening,

[REDACTED] The Screening Visit

should occur the same day as the Baseline Visit.

[REDACTED]

[REDACTED] The study eye and non-study eye, as well as binocular, was evaluated at all appropriate assessments.

The subject instilled one drop once daily (QD) at or near bedtime (8PM to 10PM) in both eyes (OU) for 14 days (+ 1 day). Each subject received sufficient study medication for the duration of the trial. A study medication box was dispensed at Visit 1 (Screening/ Baseline; Day 1). The first dose of study medication was taken on the evening of the Baseline Visit (Day 1).

All opened bottles as well as any unopened study medication were returned at Visit 2 (Treatment; Day 8) and Visit 3 (Treatment; Day 15). At Visit 2, the box was re-dispensed to the subject following study drug accountability and removal of opened study medication materials. Study medication accountability was conducted at Visit 3, but the box was not re-dispensed.

Up to 3 days after Visit 3, a follow-up phone call (Visit 4) was completed. Subjects were asked if they had any problems with their eyes from the last visit, including whether their eyes are red, and if there have been any changes in their medical condition or concomitant medications since their last visit. There was no treatment administered at Visit 4.

The schedule for assessments and timing of events is presented in [Table 1](#).

Table 1 Screening, Baseline, Treatment, and Follow-Up Visits and Procedures Schedule

Abbreviations: BAT, Brightness Acuity Tester; BCDVA, best-corrected distance visual acuity; CCLRU, Cornea and Contact Lens Research Unit; DCNVA, distance-corrected near visual acuity; mLcVA, mesopic low-contrast visual acuity

5.2. Inclusion – Exclusion Criteria and General Study Population

The study population will be approximately 160 DLD subjects ≥ 18 years of age, with approximately 136 evaluable subjects. Written informed consent will be obtained from each subject.

The inclusion and exclusion criteria defined in the protocol apply to all subjects and are not repeated herein the SAP. Reference is made to the final protocol for the specific inclusion and exclusion criteria for study subjects.

5.3. Randomization and Blinding

A randomization code for allocating subjects to treatment will be prepared by a masked biostatistician not connected with the study. At the initiation of study-related procedures, every subject who is screened is assigned a subject identification number in numerical order within site. Once a subject is qualified for the study, the subject is assigned a randomization number in the order provided by the biostatistician, and randomized into the study.

Treatment randomization will be 1:1, Nyxol or Placebo (vehicle), [REDACTED]
[REDACTED] It is assumed that there will be approximately 15% drop-out between Day 1 and Day 15.

The study medication will be masked to investigators, study staff, study subjects, the clinical research organization, and Ocuphire. Only in case of medical emergency or occurrence of serious adverse events (SAEs) will the randomization code be unmasked by the study pharmacist and made available to the Investigator, Ocuphire, and/or other personnel involved in the monitoring or conduct of this study. Rules for unmasking a subject for safety reasons are fully described in the protocol and not repeated herein this SAP.

5.4. Analysis Variables

Variables to be summarized include demographics and baseline characteristics, medical (non-ocular) and ocular history, concomitant medications, and study drug accountability.

Efficacy variables include:

- Mesopic low-contrast BCDVA (mLCVA)
- Photopic low-contrast BCDVA (pLCVA)
- Mesopic high-contrast BCDVA (mHCVA)
- Mesopic high-contrast DCNVA
- Photopic pupil diameter

- Mesopic pupil diameter
- Total RMS error (score) and higher-order RMS (spherical, coma, trefoil) error
- Subject questionnaire

Safety variables include:

- Conjunctival hyperemia (eye redness) measured with a CCLRU card 4-point scale:
 - None (0) = Normal Appears white with a small number of conjunctival blood vessel easily observed.
 - Mild (+1) = Prominent, pinkish-red color of both the bulbar and palpebral conjunctiva.
 - Moderate (+2) = Bright, scarlet red color of the bulbar and palpebral conjunctiva.
 - Severe (+3) = Beefy red with petechiae, dark red bulbar and palpebral conjunctiva with evidence of subconjunctival hemorrhage.
- AEs
- Vital signs (HR and BP)
- IOP
- Biomicroscopy
- Ophthalmoscopy
- Urine pregnancy tests for females of childbearing potential

6. SAMPLE SIZE

A sample size of approximately 136 subjects that are evaluable for efficacy (68 per treatment group) is needed for the study.

A large rectangular area of the page is completely blacked out, indicating that the corresponding text has been redacted.

It is assumed that there will be approximately 15% drop-out between Day 1 and Day 15. To account for this drop-out, a total of approximately 160 subjects will be randomized into the study.

7. GENERAL CONSIDERATIONS

7.1. Analysis Populations

The following analysis populations will be defined for this study.

7.1.1. Modified Intention-to-Treat (mITT)

The mITT will include all randomized subjects who received at least 1 dose of study medication and have a Baseline and any Day 8 efficacy measurement. The mITT will be used for the primary endpoint analysis and to analyze efficacy endpoints, with subjects included in their randomized treatment regardless of the treatment they actually received.

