9.2 Analysis Populations

Modified Intention-to-Treat: The mITT will include all randomized subjects who received at least 1 dose of study medication. The mITT will be used for the primary endpoint analysis and to analyze efficacy endpoints.

Per Protocol Population: The PP population includes all subjects in the mITT who received at least 5 doses of study medication during the first 7 days of dosing including the day prior to Day 8, have a Baseline and a Day 8 mLcVA measurement, and have no major protocol deviations. The PP population will be used to analyze efficacy endpoints.

All Randomized Population (ARP): The ARP will include all randomized subjects. This population is also known as the intention-to-treat (ITT) population. The ARP will be used in confirmatory efficacy analyses.

Safety Population (SP): The SP will include all randomized subjects who have received at least 1 dose of study medication. The SP will be used to summarize safety variables.

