Efficacy will be assessed using the mITT and PP population with subjects included in the treatment arm in which they were randomized. For the analysis of the primary efficacy endpoint, appropriate imputation techniques will be performed for missing observations if applicable; details will be provided in the study Statistical Analysis Plan. If the analysis using the PP population shows a positive effect for Nyxol at the 0.05 level of significance, the primary endpoint will be considered met. Confirmatory analyses may be performed using the ARP, with imputation performed for missing data. For the analysis of the secondary efficacy endpoints, only observed case data will be used. If warranted, confirmatory analyses using the ARP with imputation for missing data will also be performed for the secondary efficacy endpoints.

For all efficacy endpoints, Baseline values are defined as the screening assessment values on Visit 1 (Day 1).

Secondary efficacy endpoints are indicated in [Section 4.1](#).

Each of the continuous secondary efficacy endpoints will be analyzed using analysis of covariance (ANCOVA) with change from baseline as the dependent variable, treatment, [REDACTED], and the respective baseline value included as the covariate. Each ANCOVA will be performed using the mITT and PP population, with subjects included in their randomized treatment regardless of the treatment they actually received. The output from each ANCOVA will include the least squares mean (LSM) and standard error for both treatment groups, along with the placebo-corrected LSM, its 95% CI and associated p-value.

For each of the secondary endpoints related to percent of subjects achieving certain criteria, the analysis will be performed using a logistic regression model with treatment, light/dark irides, and the respective baseline as a covariate. For each analysis, the percentage of subjects in each treatment group meeting the criteria, the OR with 95% CI and p-value will be provided. For these endpoints, the mITT and PP population will be used with subjects included in their randomized treatment regardless of the treatment they actually received.

In addition, each secondary efficacy endpoint will be analyzed [REDACTED] using the same model and sensitivity analysis indicated above, as appropriate. Other subgroups, such as age, sex, and race, may be analyzed as well.

9.3.6 *Analysis of Safety*

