7.3.2. Missing Data

The primary efficacy endpoint is the percent of subjects with ≥ 15 ETDRS letters (≥ 3 lines) of improvement in the study eye compared to baseline in monocular mLcVA at Day 8. For the analysis of the primary efficacy endpoint, imputation will be performed for missing efficacy data as specified in [Section 7.3.2.3](#) for the analysis using the mITT. Confirmatory analyses will be performed using the ARP, also using imputation for missing data.

Otherwise, there will be no substitutions made to accommodate missing data points for efficacy data. All data recorded on the CRF will be included in data listings that will accompany the CSR.

Safety data will be imputed in limited situations. If the severity of an AE is missing, then the severity will remain missing. If relationship of the AE to study drug is missing, the relationship will remain missing. Missing or partial dates for AEs or concomitant medications will be imputed as described in [Section 7.3.2.1](#). Otherwise, all summaries of safety endpoints will be completed using observed cases in the SP; no imputation will be completed.

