7.3.2.2. Missing Baseline Data

Every effort will be made to ensure that accurate baseline information on the subjects is collected. In the event that a subject is missing baseline information, the subject will be included in the SP for assessment of safety and excluded from the primary analyses. Each case of missing baseline data will be evaluated for potential inclusion in the exploratory endpoints. All baseline data will be observed cases, without imputation.

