7.3.2.3. Imputation Methods

[REDACTED]

[REDACTED]

[REDACTED]

[REDACTED]

The imputations will be done separately for each treatment group and will include the following variables in the imputation model: mLcVA at baseline and Day 8.

The number of imputations [REDACTED]. The change from baseline will be calculated from these imputed datasets. The observed outcome ([REDACTED]) for each imputed dataset will be [REDACTED]. See [Section 9.1](#) for details on these models. The estimates

and standard errors (SEs) of the odds ratios based on the

Example SAS code is provided below:

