9. EFFICACY ANALYSES

Unless otherwise noted, efficacy will be assessed using the mITT and PP populations, with subjects included in their randomized treatment regardless of the treatment they actually received. For the analysis of the primary efficacy endpoint, imputation will be performed for missing data as described in [Section 7.3.2.3](#). If the analysis using the mITT Population shows a positive effect for Nyxol at the 0.05 level of significance, the primary endpoint will be considered met.

Confirmatory analysis of the primary efficacy endpoint will be performed using the ARP, also using imputation for missing data. For the analysis of the secondary efficacy endpoints, only observed case data will be used.

To formally test the significance of endpoints of interest beyond primary efficacy, endpoints will be tested in a predefined sequence using observed data only, each at the significance level 0.05, until the first nonsignificant test. The primary efficacy endpoint will be first in this sequence. The endpoints in the sequence are for the mITT population and study eye, and either Day 8 or Day 15. The sequence is specified in [Section 12.3](#).

All efficacy assessment data, regardless of whether they are included in the analysis, will be presented in by-subject listings.

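### SAP 7.1.1 adds a Day 8 measurement condition to the protocol's mITT, so the imputation planned for the deciding analysis cannot reach dosed subjects with no Day 8 data

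*SAP*

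**What the plan says.** **Definition.** Protocol 9.2 states: "The mITT will include all randomized subjects who received at least 1 dose of study medication". It sets no measurement condition and assigns this set to the primary analysis. SAP 7.1.1 gives the same name and use to "all randomized subjects who received at least 1 dose of study medication and have a Baseline and any Day 8 efficacy measurement".

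**Deciding population.** SAP 9 counts the primary endpoint as met on this condition: "If the analysis using the mITT Population shows a positive effect for Nyxol at the 0.05 level of significance". Protocol 9.3.5 has the same sentence with another population: "If the analysis using the PP population shows a positive effect for Nyxol at the 0.05 level of significance".

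**Missing data.** SAP 7.3.2 states, for the mITT: "For the analysis of the primary efficacy endpoint, imputation will be performed for missing efficacy data". The method in SAP 7.3.2.3 is largely redacted. The visible text says that imputation is done by treatment group and that the model "will include the following variables in the imputation model: mLcVA at baseline and Day 8". Under SAP 7.3.2.2, if baseline is missing, "the subject will be included in the SP for assessment of safety and excluded from the primary analyses". SAP 7.3.2 and 9 also require a confirmatory analysis of all randomized subjects (ARP) with imputation.

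**Test sequence.** In SAP 9, "endpoints will be tested in a predefined sequence using observed data only", with the primary endpoint first.

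**Declared changes.** The visible part of SAP 3.3 lists the hierarchy, the handling of the questionnaire and two added secondary endpoints. It then says that the analyses otherwise agree with the protocol.

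**The concern.** Having a Day 8 measurement is a post-randomization event at the primary timepoint. Making it a condition of entry to the deciding set removes the subjects for whom imputation matters most, namely those who were dosed and left before giving any Day 8 data. The plan promises to handle missing primary data in that set, and its own population rule takes most of those data out of scope.

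If the excluded subjects differ from those who stay, and the difference is not the same in both arms, the deciding comparison no longer has the full protection of randomization. The Baseline condition is a lesser matter. Baseline mLCVA is needed for eligibility, and SAP 7.3.2.2 already excludes subjects without it from the primary analyses.

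**Working it through.** **1. The plan's own figure.** Inputs: 136 evaluable subjects and 15% drop-out (Protocol 9.1; SAP 6).

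136 / (1 − 0.15) = 160, which matches the stated number to randomize. The allowance is 160 − 136 = 24 subjects, and 24 / 160 = 15%. Protocol 9.1 defines evaluable as having a Day 8 mLCVA, so 24 is the planned number without one.

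**2. Who is where.** For randomized subjects with a baseline:

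| Subject | Protocol 9.2 mITT | SAP 7.1.1 mITT | Primary result imputed in SAP mITT? | ARP |
|---|---|---|---|---|
| Dosed, Day 8 study-eye mLCVA present | in | in | not needed | in |
| Dosed, no Day 8 study-eye mLCVA, other Day 8 efficacy data | in | in | yes | in |
| Dosed, nothing mapped to Day 8 | in | **out** | **no** | in |
| Never dosed | out | out | no | in |

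Only the third row changes between the two definitions.

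**3. How many.** If 0%, 25%, 50%, 75% or 100% of the 24 are in the third row, 0, 6, 12, 18 or 24 subjects leave, and the SAP mITT is 160, 154, 148, 142 or 136 (all subjects dosed). The top of this range is unlikely for four reasons:
- SAP 6 spreads the 15% over Day 1 to Day 15, so some loss comes after Day 8.
- SAP 7.3.3 can map early-termination data to Day 8.
- Protocol 4.9.4 asks sites to obtain the Day 8 measurements before a subject leaves.
- The first dose is taken at home, so some losses may be never-dosed subjects, whom both definitions exclude.

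**4. What it could do to the test.** All rates here are assumptions, because the documents give no loss by arm and the design response rates are not visible. The simulation uses 80 per arm, a true response of 10% in both arms, a two-sided pooled z-test at 5%, and only subjects with observed Day 8 data. Loss is a share of the whole arm and falls only on non-responders, so each non-responder is lost with probability (arm loss) / 0.9. The expected observed response is about 0.10 / (1 − arm loss). At 30% loss that is 0.10 / 0.70 = 14.3%, against 10% in an arm with no loss.

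| Arm loss, Nyxol / placebo | Subjects lost | Type I error |
|---|---|---|
| 15% / 15% | 12 + 12 = 24 | 5.0% |
| 20% / 10% | 16 + 8 = 24 | 5.8% |
| 15% / 0% | 12 + 0 = 12 | 6.5% |
| 30% / 0% (extreme) | 24 + 0 = 24 | 12.5% |

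When loss is unrelated to outcome, the error stays at 4.9% to 5.0% even at 30% / 0%.

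**5. What restoring the definition recovers.** The imputation method is redacted, so this step assumes within-arm regression imputation from baseline, a baseline-to-Day 8 correlation of 0.5, and 20 imputations. In the extreme 30% / 0% case, bias in the response difference falls from 4.4 to 3.6 percentage points, about one fifth. Type I error falls from 11.8% to 7.9%. Part of that fall is conservative variance rather than removed bias: with loss unrelated to outcome, the error falls from 5.2% to 3.9% at 0% / 30% and from 4.9% to 4.2% at 0% / 15%.

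**The case against.** - **The SAP improves on the protocol.** Protocol 9.3.5 decides on PP, which requires a Day 8 mLCVA, at least 5 doses in the first week and no major deviations. The SAP's deciding set is wider. This stands, so a reader who infers that the SAP narrowed the deciding analysis overall would be wrong. What was narrowed is the mITT, which Protocol 9.2 itself assigns to the primary analysis.
- **Day 8 data are part of the protocol's own thinking.** Protocol 9.1 ties evaluability to a Day 8 mLCVA, and Protocol 9.4 focuses on observed cases. This shows that the protocol is not of one mind. But evaluability there is a sample-size term, and Protocol 9.2 does not carry it into the mITT.
- **The ARP analysis covers it.** It includes every excluded subject, and the SAP requires it where Protocol 9.3.5 only allowed it. Among subjects with a baseline, the restored mITT is the ARP less the never-dosed. This limits the harm substantially, but the ARP result does not decide success.
- **No unequal loss is in prospect.** Protocol 2.2 reports good tolerability, and moderate splits give 5.0% to 6.5%. This also stands. The documents neither predict nor exclude unequal, outcome-related loss.
- **Redaction and version.** Part of SAP 3.3 is missing, directly after it announces the two added endpoints, so the changes can only be called not visible there. The SAP is written to protocol amendment 3, and the supplied protocol cannot be confirmed as that version.

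**Conclusion.** The mismatch is plain on the text. SAP 7.1.1 conditions the deciding set on Day 8 data, and the imputation promised for that set cannot reach dosed subjects with none. The deciding population also differs between the documents, and SAP 3.3 as visible shows neither change. This should be fixed, but it does not threaten the trial. At most about 24 of 160 subjects are involved, probably fewer, and the effect on the test is small unless loss is both markedly unequal and related to outcome. The 12.5% figure belongs to an extreme assumed case.

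Three stronger readings are tempting and are not supported:
- A reader might infer that imputation in the mITT is empty. It is not, because a subject with other Day 8 efficacy data can still be imputed.
- A reader might infer that restoring the definition would cure bias from outcome-related loss. It removes only a small part.
- A reader might infer that the plan lacks a sensitivity analysis for departures from its missing-data assumption, such as a tipping-point analysis. The methods text is redacted, so its absence cannot be shown.

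**What to change.** 1. In SAP 7.1.1, restore the Protocol 9.2 definition (randomized, at least one dose) for the primary analysis, and leave missing baseline to SAP 7.3.2.2. The imputation in SAP 7.3.2.3 then covers dosed subjects with no Day 8 data. Keep the Day 8-observed set as a sensitivity analysis.
2. Reconcile Protocol 9.3.5 with SAP 9, state that the mITT decides, and list both the definition and the deciding population in SAP 3.3.
3. State in SAP 9 that the analysis that decides the primary endpoint also opens the test sequence. The sequence now uses observed data only, and after step 1 the imputed and observed-only primary results could differ by up to about 24 subjects.

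The cost is SAP wording, a population flag and one sensitivity table, with no new data. SAP 3.1 has the plan finalized before unmasking, so the change belongs before then. The downside is that more of the deciding result rests on imputed values. Multiple imputation by arm may also be slightly conservative, with some loss of power.
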